#### **11.2.2 SAEs (Including Deaths) and Adverse Events Leading to Study Drug Discontinuation**

Deaths, AE leading to study drug discontinuation, and all SAEs will be presented in listing format. A listing of all pretreatment (i.e., events start prior to the first study drug injection) serious adverse events will be provided.

The following summaries of AEs by SOC and PT will be generated:

- Any SAE
- Any SAE with causal relationship to study drug
- Any TEAE leading to discontinuation of study drug
- Any TEAE leading to discontinuation of study drug with causal relationship to study drug

## **11.3 Analysis of Laboratory Data**

Listing and descriptive statistics of laboratory values over time and extreme abnormal value on treatment will be provided. Baseline is the last non-missing values on or before the date of the first dose of risankizumab either in Study 1311.2 or this study. Extreme abnormal value on treatment is the on treatment laboratory value which is most significantly away from the reference range. Frequency of subjects with transitions relative to reference range and listing of subjects with significant abnormal laboratory values will be presented as well.

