7.3.3 Safety analyses

All subjects who received one dose of study drug will be included in the safety evaluation.

Safety analyses will focus on adverse events related to early discontinuation, immune suppression and injection site effects. AEs will be coded using the Medical Dictionary for Drug Regulatory Affairs (MedDRA). All AEs occurring up to 12 weeks after the last trial medication administration will be assigned to the treatment period for evaluation. The evaluation of adverse events will comprise various frequency tabulations. The additional analyses of pre-defined AESI will consider the frequency, intensity, time to first onset of the AE, duration of the AE and clinical consequences (e.g. study discontinuation).

Analysis of laboratory measures will similarly focus on hematologic measures of immune suppression. Descriptive statistics of laboratory values over time and for the difference from baseline will be provided. Frequency tables of changes with respect to the reference range between baseline and last/worst value on treatment and patients with possible clinically significant abnormalities will also be presented.

Immunogenicity will be evaluated in terms of time to antibody emergence starting from the time of first exposure to BI 655066 in either 1311.2 or 1311.13. This will be analysed using a Kaplan-Meier estimate.

Safety will also be assessed by evaluation of vital signs (BP, PR, RR, oral or tympanic body temperature) and local tolerability.

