### 11.3.2 Statistical Methods

#### Analysis of Quantitative Laboratory Parameters

Though the protocol indicates utilizing the Rheumatology Common Toxicity Criteria (RCTC) scale for grading laboratory values, given that the National Cancer Institute Common Toxicity Criteria for Adverse Events (NCI CTCAE) scale includes a more comprehensive list of laboratory values, the sponsor will present the lab analyses based on the NCI CTCAE scale. Observed values at each scheduled visit in continuous laboratory

parameters will be summarized with the mean, standard deviation, median, minimum and maximum. If there are multiple post-baseline measurements on the same day, average value will be used.

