### **Shift Tables**

Shift tables will be provided for each hematology, clinical chemistry parameter. Shifts from Baseline to the following endpoints will be considered: post-Baseline value and final value. This analysis will be performed only for category of "low or normal" at Baseline which shift to 'high' and category of "high or normal" at Baseline which shift to category of 'low.' If there are multiple post-baseline measurements on the same day, last value will be used.

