**Table 5. Criteria for Potentially Clinically Important Hematology Values**

Hematology Variables	Units	Definition of Potentially Clinically Important Current (Version 4) Grade 3 or greater	
		Very Low	
Hemoglobin	g/dL		< 8.0
Platelets count	$10^9/\text{L}$		< 50.0
White Blood Cells	$10^9/\text{L}$		< 2.0
Neutrophils	$10^9/\text{L}$		< 1.0
Lymphocytes	$10^9/\text{L}$		< 0.5

A separate listing will be provided that presents all of the subjects and values that are NCI CTCAE toxicity grade 3 or above. For each of these subjects, the whole course of the respective parameter will be listed.

If there are multiple measurements on the same day, the worst value will be used.

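### The extreme on-treatment laboratory value in SAP 11.3 has no direction, so its summary pools values below range with values above range

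*SAP*

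**What the plan says.** SAP section 11.3 promises: "Listing and descriptive statistics of laboratory values over time and extreme abnormal value on treatment will be provided". The next definition is: "Extreme abnormal value on treatment is the on treatment laboratory value which is most significantly away from the reference range". I read this as one value per patient per parameter, although the SAP does not say so. It does not say whether high and low are treated apart, how distance from the range is measured, or what is recorded for a patient who is never abnormal.

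The SAP's only explicit list of laboratory statistics is in 11.3.2, for observed values by scheduled visit: "parameters will be summarized with the mean, standard deviation, median, minimum and maximum". No separate list is given for the extreme value.

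Protocol 7.3.3 sets the emphasis: "Analysis of laboratory measures will similarly focus on hematologic measures of immune suppression". It also promises "Frequency tables of changes with respect to the reference range between baseline and last/worst value on treatment". The SAP's extreme value is the nearest counterpart to that worst value, and the protocol gives no direction either.

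Other outputs in SAP 11.3.2 do keep direction:
- The shift tables have separate to-high and to-low categories: "Shifts from Baseline to the following endpoints will be considered: post-Baseline value and final value". Which post-baseline value is meant is not stated.
- Table 5 counts low haematology values only, under the column heading "Definition of Potentially Clinically Important Current (Version 4) Grade 3 or greater". The full course is listed for patients at Grade 3 or above.

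**The concern.** A worst-value summary should show how far patients moved in the direction that matters. Here the variable can hold a low for one patient and a high for the next, and the two cancel in a mean. Within one patient, a high can also take the place of a low.

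At stake is the one planned summary of each patient's worst laboratory value. Immune suppression would naturally appear as low counts (my inference; the protocol does not name a direction), and a direction-free extreme is poorly suited to show them.

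**Working it through.** The documents give no figure that depends on this rule, so there is none to reproduce. The reference ranges are in the investigator site file (Protocol 5.2.3), so the limits below are assumptions.

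**Inputs**
- Lower limits (LLN), from the upper edge of the Grade 1 bands in Protocol 10.7: neutrophils 2.0 (Grade 1 is 1.5 to 1.9) and WBC 4.0 (Grade 1 is 3.0 to 3.9).
- Upper limits (ULN), assumed: neutrophils 7.0 to 8.0, WBC 10 to 12.
- Table 5 thresholds: neutrophils below 1.0, WBC below 2.0.

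**1. Pooling across patients.** Ten patients with an extreme neutrophil count of 1.0 and ten with 9.0:

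mean = (10 × 1.0 + 10 × 9.0) / 20 = 100 / 20 = 5.0

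This lies inside the assumed range although all 20 values are outside it. None of the ten lows enters Table 5, because 1.0 is not below 1.0. With the same ten lows but only two highs, the mean is (10 × 1.0 + 2 × 9.0) / 12 = 28 / 12 = 2.3. The low-count experience is unchanged, yet the mean moves from 5.0 to 2.3 because of the highs alone. The median does little better. In the ten-and-ten case it is (1.0 + 9.0) / 2 = 5.0; otherwise it mainly reports which tail has more patients.

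**2. Displacement within a patient.** Let L be the lowest and H the highest value.

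| Distance scale | H displaces L when | Neutrophils, L = 1.0 | WBC, L = 2.0 |
|---|---|---|---|
| Absolute | H > ULN + LLN − L | H > 8.0 to 9.0 | H > 12 to 14 |
| Ratio | H > ULN × LLN / L | H > 14 to 16 | H > 20 to 24 |

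On the absolute scale a low can be at most LLN units out of range, while highs have no bound, so a neutrophil count of 0 is displaced by any H above 9.0 to 10.0. On the ratio scale a count of 0 is infinitely far out and is never displaced. The missing scale therefore decides the result.

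**3. Simulation under assumed variability.** 200,000 patients with 17 post-baseline neutrophil counts each (Extended Visits 2 to 18), log-normal, median 4.0, between-patient log-SD 0.25:

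| Within-patient log-SD | Low displaced, absolute (% of patients with a low) | Low displaced, ratio | Mean extreme value, absolute |
|---|---|---|---|
| 0.2 | 0 to 0.1 | 0 | 5.5 to 6.2 |
| 0.3 | 4 to 11 | 3 to 7 | 5.9 to 6.3 |
| 0.4 | 27 to 43 | 16 to 27 | 6.8 to 7.4 |

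Ranges run over ULN 7.0 to 8.0. The mean is inside the assumed range in eight of the nine settings; the exception is ULN 7.0 with log-SD 0.4. That last row gives 52% of patients a low and 52 to 68% a high. Other assumptions (12 visits, between-patient log-SD 0.30 to 0.35, within-patient 0.25 to 0.30) give displacement in 0.2 to 5.8% of patients with a low, and a mean extreme value of 5.7 to 6.4.

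Pooling appears in every setting where both tails occur. Displacement runs from nil to substantial, depending on what is assumed.

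**The case against.** The best defence is that the extreme value is one line among several. The to-low shift tables have no grade threshold, so milder lows are within their scope. The by-visit summaries report the minimum at each visit. Table 5 counts low values, and severe cases are listed in full. SAP 11.3 also adds frequencies of transitions relative to the reference range. All of this stands, with two limits: the shift tables capture a transient low only if the post-baseline value means any or the lowest value, and patients already low at baseline are outside the to-low shift.

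It can also be said that mean and SD are spelled out only for by-visit values. That is correct. If the same list is used for the extreme value, the minimum and maximum would hint at the mixture: 1.0 and 9.0 in the example. They would not show how many patients lie on each side.

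A reader might infer that the laboratory analysis cannot show immune suppression at all. The documents do not support this, because the outputs above are direction-specific or report minima. A reader might also infer that a high peak always overrides even a count of zero. That holds only on an absolute scale, which the SAP does not state.

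**Conclusion.** The concern holds for this summary. As written, the rule puts opposite abnormalities into one variable for every test with two limits, and a mean of it cannot be interpreted. That conclusion rests on the plain reading of a definition without direction, not on the simulation. The figure of 5.0 illustrates it and depends on assumed limits.

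Displacement of a low by a high is the lesser defect. Its frequency, about 0 to 43% of patients with a low neutrophil count across all settings tried, is a statement about assumptions and not an estimate for this trial.

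The values most exposed are lows milder than Grade 3, which Table 5 does not count. They leave this summary, not the report. The study is descriptive and plans no tests, so no formal inference is affected. The point still merits a change, because it alters a reported result, touches the protocol's stated laboratory focus and costs very little.

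**What to change.** In SAP 11.3, replace the single extreme value with two variables per patient and parameter: the minimum and the maximum on-treatment value. Summarise each separately, with the number of patients below LLN for the minimum and above ULN for the maximum. Present the minimum first for WBC, neutrophils, lymphocytes and platelets.

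In the shift tables of SAP 11.3.2, define the post-baseline value the same way: the minimum for shifts to low and the maximum for shifts to high.

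By construction, no low is then displaced by a high and the two tails are never averaged together. The cost is SAP wording and one extra derived variable per test, with no new data. SAP 3.0 places sign-off before database lock, so the change should be made by then.

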### **11.3.1 Variables and Criteria Defining Abnormality**

Clinical laboratory tests performed are listed in [Table 3](#).

**Table 3. Clinical Laboratory Tests**

Category	Test name
Haematology	Hematocrit (Hct) Hemoglobin (Hb) Red Blood Cell Count/Erythrocytes Reticulocyte Count Glycosylated Hbc (HbA1c) White Blood Cells/Leukocytes Platelet Count/Thrombocytes
Diff. Automatic	Neutrophils (relative and absolute count) Eosinophils (relative and absolute count) Lymphocytes (relative and absolute count) Basophils (relative and absolute count) Monocytes (relative and absolute count)
Diff Manual (if Diff Automatic is abnormal)	Neutrophils, Bands (Stabs) Neutrophils, Polymorphonuclear (PMN) Eosinophils Basophils Monocytes Lymphocytes
Enzymes	Aspartate Aminotransferase/Glutamate-Oxaloacetate Transaminase (AST/GOT) Alanine transaminase (Glutamic Pyruvate Transaminase (ALT/GPT) Alkaline Phosphatase (AP/ALP) Creatine Kinase (CK) CK-MB if CK is elevated Lactic Dehydrogenase (LDH)
Coagulation	Partial Thromboplastin Time (= aPTT) Prothrombin Time (Quick and International normalised ratio (INR))
Electrolytes	Calcium Sodium Potassium

**Table 3. Clinical Laboratory Tests (Continued)**

Category	Test name
Substrates	Glucose Creatinine Blood urea nitrogen Bilirubin Total Bilirubin Direct Protein, Total C-Reactive Protein (CRP) Uric Acid Cholesterol, total High density lipoprotein (HDL) Cholesterol Calculated low density lipoprotein (LDL) Cholesterol Triglycerides
Urinalysis (Stix)	Urine Nitrite Urine Protein Urine Glucose Urine Ketone Urobilinogen Urine Bilirubin Urine RBC/Erythrocyte Urine WBC/Leukocytes Urine pH Urine albumin (microalbumin urine test) (roll-over visit only)
Urine-Sediment (microscopic examination) (if urine analysis abnormal)	Urine Sediment Bacteria Urine Cast in Sediment Urine Squamous Epith Cells Urine Sediment Crystals, Unspecified Urine Sediment red blood cell count (RBC)/Erythrocytes Urine Sediment white blood cell count (WBC)/Leucocytes

### 11.3.2 Statistical Methods

#### Analysis of Quantitative Laboratory Parameters

Though the protocol indicates utilizing the Rheumatology Common Toxicity Criteria (RCTC) scale for grading laboratory values, given that the National Cancer Institute Common Toxicity Criteria for Adverse Events (NCI CTCAE) scale includes a more comprehensive list of laboratory values, the sponsor will present the lab analyses based on the NCI CTCAE scale. Observed values at each scheduled visit in continuous laboratory

parameters will be summarized with the mean, standard deviation, median, minimum and maximum. If there are multiple post-baseline measurements on the same day, average value will be used.

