5.2.3 Assessment of safety laboratory parameters

The laboratory parameters that will be determined are listed in [Tables 5.2.3: 1](#) and [5.2.3: 2](#) at the time points provided in [Flow Chart](#). The respective reference ranges will be provided in the ISF. The laboratory tests will be performed at a designated central laboratory, and if necessary by additional specialist laboratories.

Laboratory results of the patients will be available in real time to the respective investigator and to the clinical monitor of each country (central laboratory website), and selected

Proprietary confidential information.

© 2018 Boehringer Ingelheim International GmbH or one or more of its affiliated companies. All rights reserved.

This document may not - in full or in part - be passed on, reproduced, published or otherwise used without prior written permission.

abnormal laboratory alerts will be sent automatically to the sites and to the sponsor in real time. PK, PD and biomarker data will not be available to the investigators or local clinical monitors, but only to the Trial Team (sponsor) and to the DMC.

Clinically relevant laboratory values will be commented on in the eCRF. A clinically relevant value may be either in- or outside the reference range. Clinically relevant abnormal laboratory test results must be repeated using an unscheduled visit lab kit and must be repeated until normalisation or stabilisation or until an alternative explanation has been found. Clinically relevant abnormal laboratory values will be also graded for intensity by using RCTC Version 2.0 criteria.

The tests listed in Table 5.2.3: 1 constitute laboratory tests and hormones (assessed in female patients only) that will be done only at the initial roll-over visit and at Extended EOT or Extended EOS after approval of amendment # 5 and start of the rollover of patients to the M15-997 study from 01-May-2018, i.e. these tests are only required at EV1 for patients that are having EV1 as their first 1311.13 visit. The results will not be included into the report. Samples will be archived and run as clinically necessary.

Table 5.2.3: 1 Exclusionary Testing

Category	Test name
Tb screening	Interferon-gamma release assay (IGRA)
Serum pregnancy test (only female patients of childbearing potential)	Serum β -Human Chorionic Gonadotropin

Table 5.2.3: 2 Safety laboratory tests

Category	Test name

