I-10. Seizure	NA	Recurrence of old seizures, controlled with adjustment of medication	Recurrence/exacerbation with partial response to medication	Recurrence not controlled, requiring hospitalization; new seizures	
I-11. Vertigo (dizziness)	Subjective symptoms, transient, intermittent, no treatment	Objective findings, recurrent, meds relieve, occasionally interfering with function	Persistent, prolonged, interfering with daily function; partial response to medication	Debilitating without response to medication, hospitalization	
J. PULMONARY					
J1. Asthma	Occasional wheeze, no interference with activities	Wheezing, requires oral meds, occasional interference with function	Debilitating, requires nasal O ₂	Requires ventilator assistance	
J2. Cough	Transient, intermittent, occasional OTC meds relieve	Persistent, requires narcotic or other prescription meds for relief	Recurrent, persistent coughing spasms without consistent relief by meds, interferes with function	Interferes with oxygenation; debilitating	

	1 - Mild	2 - Moderate	3 - Severe	4 - Includes Life Threatening
J. PULMONARY				
J3. Dyspnea	Subjective, transient, no interference with function	Symptomatic, intermittent or recurring, interferes with exertional activities	Symptomatic during daily routine activities, interferes with function, treatment with intermittent nasal O ₂ relieves	Symptomatic at rest, debilitating, requires constant nasal O ₂
J4. Pleuritic pain (pleurisy)	Transient, intermittent symptoms, no treatment or OTC meds relieve	Persistent symptoms, requires prescription meds for relief	Prolonged symptoms, interferes with function, requires frequent narcotic pain relief	Debilitating, requiring hospitalisation
J5. Pneumonitis (pulmonary infiltrates)	Asymptomatic radiographic changes, transient, no treatment required	Symptomatic, persistent, requiring corticosteroids	Symptomatic, requiring treatment including O ₂	Debilitating, not reversible; or requiring assisted ventilation

	1 - Mild	2 - Moderate	3 - Severe	4 - Includes Life Threatening
J. PULMONARY				
J6. Pulmonary function decreased (Forced vital capacity (FVC) or carbon monoxide diffusion capacity—DLCO)	76–90% of pre-treatment value	51–75% of pre-treatment value	26–50% of pre-treatment value	≤25% of pre-treatment value
LABORATORY DATA				
K. HAEMATOLOGY				
K1. Hgb (g/dl) decrease from pre-treatment	1.0–1.4	1.5–2.0	2.1–2.9; or Hgb < 8.0, > 7.0	≥3.0; or Hgb < 7.0
K2. Leukopenia (total WBC) x 1000	3.0–3.9	2.0–2.9	1.0–1.9	< 1.0

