K3. Neutropenia (x 1000)	1.5–1.9	1.0–1.4	0.5–0.9	< 0.5

	1 - Mild	2 - Moderate	3 - Severe	4 - Includes Life Threatening
LABORATORY DATA				
K. HAEMATOLOGY				
K4. Lymphopenia (x 1000)	1.5–1.9	1.0–1.4	0.5–0.9	< 0.5
K5. Platelets (x 1000)	75– Lower limit of normal (LLN)	50–74.9	20–49.9; platelet transfusion required	< 20; recurrent platelet transfusions
LABORATORY DATA A				
L. CHEMISTRY				
L1. Hypercalcaemia (mg/dl)	1.1 x ULN–11.5	11.6–12.5	12.6–13.5; or symptoms present	> 13.5; or associated coma
L2. Hyperglycaemia (mg/dl) Fasting	140–160	161–250	251–500	>500, or associated with fasting ketoacidosis

	1 - Mild	2 - Moderate	3 - Severe	4 - Includes Life Threatening
LABORATORY DATA				
L. CHEMISTRY				
L3. Hyperkalaemia (mg/dl)	5.5–5.9	6.0–6.4	6.5–7.0 or any ECG change	> 7.0 or any arrhythmia
L5. Hypocalcaemia (mg/dl)	0.9 x LLN–7.8	7.7–7.0	6.9–6.5; or associated with symptoms	< 6.5, or occurrence of tetany
L6. Hypoglycemia (mg/dl)	55–64 (no symptoms)	40–54 (or symptoms present)	30–39 (symptoms impair function)	< 30, or coma
L7. Hyponatraemia (mg/dl)	NA	125–129	120–124	< 120
L8. Hypokalaemia (mg/dl)	NA	3.0–3.4	2.5–2.9	< 2.5
L9. CPK (also if polymyositis- disease)	1.2–1.9 x ULN	2.0–4.0 x ULN	> 4.0 x ULN with weakness but without life-threatening signs or symptoms	> 4.0 x ULN with signs or symptoms of rhabdomyolysis or life-threatening

	1 - Mild	2 - Moderate	3 - Severe	4 - Includes Life Threatening
LABORATORY DATA				
L. CHEMISTRY				
L10. Serum uric acid	1.2–1.6 x ULN	1.7–2.9 x ULN	3.0–5.0 x ULN or gout	NA
L11. Creatinine (mg/dl)	1.1–1.3 x ULN	1.3–1.8 x ULN	1.9–3.0 x ULN	> 3.0 x ULN
L12. SGOT (AST)	1.2–1.5 x ULN	1.6–3.0 x ULN	3.1–8.0 x ULN	> 8.0 x ULN
L13. SGPT (ALT)	1.2–1.5 x ULN	1.6–3.0 x ULN	3.0–8.0 x ULN	> 8.0 x ULN
L14. Alkaline phosphatase	1.1–2.0 x ULN	1.6–3.0 x ULN	3.0–5.0 x ULN	> 5.0 x ULN
L15. T. bilirubin	1.1–1.4 x ULN	1.5–1.9 x ULN	2.0–3.0 x ULN	> 3.0 x ULN
L16. LDH	1.3–2.4 x ULN	2.5–5.0 x ULN	5.1–10 x ULN	> 10 x ULN

	1 - Mild	2 - Moderate	3 - Severe	4 - Includes Life Threatening
LABORATORY DATA				
M. URINALYSIS				
M1. Haematuria	Micro only	Gross, no clots	Clots, transfusion < 2 units	Transfusions required
M2. Proteinuria (per 24 h)	300–500 mg (tr/1+)	501–1999 mg (2+)	2–5.0 mg (3+) nephrotic syndrome	> 5.0 g (4+) anasarca
M3. WBC in urine	NA	NA	Indicating acute interstitial nephritis	Associated with acuterenal failure

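### SAP 11.3.2's CTCAE Grade 3+ cut-offs leave values that the protocol's RCTC appendix grades as severe uncounted for seven of the 17 tests in Tables 4 and 5

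*SAP*

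**What the plan says.** Protocol 5.2.3 sets the scale: "Clinically relevant abnormal laboratory values will be also graded for intensity by using RCTC Version 2.0 criteria". Appendix 10.7 prints that scale. Its lymphocyte row, Grades 1 to 4 in order, reads "K4. Lymphopenia (x 1000) 1.5–1.9 1.0–1.4 0.5–0.9 < 0.5". Its Grade 3 entry for haemoglobin, expressed first as a fall from pre-treatment, is "2.1–2.9; or Hgb < 8.0, > 7.0". Protocol 7.3.3 says where the emphasis lies: "Analysis of laboratory measures will similarly focus on hematologic measures of immune suppression". The same section asks for a table of patients with possibly clinically significant abnormalities, but names no scale or cut-off for it.

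SAP 11.3.2 acknowledges that the protocol specifies RCTC and changes scale because the CTCAE "scale includes a more comprehensive list of laboratory values, the sponsor will present the lab analyses based on the NCI CTCAE scale". The frequency tables of potentially clinically significant values use CTCAE version 4 Grade 3 or greater (Tables 4 and 5). The listing follows the same rule: "A separate listing will be provided that presents all of the subjects and values that are NCI CTCAE toxicity grade 3 or above". SAP 11.2.1 keeps RCTC for adverse event severity.

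The SAP also plans values over time and the extreme abnormal value on treatment (11.3), and visit-wise means, medians, minima and maxima, reference-range shift tables and a listing of possible Hy's Law cases (11.3.2).

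**The concern.** A Grade 3 under one scale need not be a Grade 3 under the other. Where the SAP limit is looser than the RCTC Grade 3 limit, a patient with a value the protocol calls severe is not counted in the table intended to show notable values. Lymphocytes matter most, because the protocol directs laboratory analysis to haematologic signs of immune suppression. Liver tests come next, because hepatic injury is an adverse event of special interest.

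Two scales in one report also produce mismatches. An ALT of 4 times ULN that the investigator judges clinically relevant is an RCTC Grade 3 adverse event, yet it is absent from Table 4 and from the Grade 3+ listing.

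Safety is the primary objective in Protocol 2.2, and the trial is descriptive throughout. The count tables are therefore a main product of the trial, not a supplement to a test.

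**Working it through.** The plan gives no figure to reproduce. The check sets Appendix 10.7 (sections K and L) beside SAP Tables 4 and 5.

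**Tests where the SAP limit is looser.** Cell counts are in 10⁹/L (the appendix prints x 1000), haemoglobin in g/dL, the rest in multiples of ULN.

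| Test | RCTC Grade 3 | SAP cut-off | RCTC Grade 3+ values not counted |
|---|---|---|---|
| Lymphocytes | 0.5–0.9 | < 0.5 | 0.5–0.9 (all of Grade 3) |
| Total bilirubin | 2.0–3.0 | > 3.0 | 2.0–3.0 (all) |
| ALP | 3.0–5.0 | > 5.0 | 3.0–5.0 (all) |
| Creatinine | 1.9–3.0 | > 3.0 | 1.9–3.0 (all) |
| AST | 3.1–8.0 | > 5.0 | 3.1–5.0 |
| ALT | 3.0–8.0 | > 5.0 | 3.0–5.0 |
| Haemoglobin | fall 2.1–2.9, or value between 7.0 and 8.0 | < 8.0 | any fall of 2.1 or more with value at or above 8.0 |

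In the first four rows the SAP cut-off is the RCTC Grade 4 limit. For haemoglobin the gap reaches into Grade 4 (a fall of 3.0 or more, or a value below 7.0):
- 15.0 − 12.5 = 2.5: RCTC Grade 3, not flagged by the SAP.
- 15.0 − 11.5 = 3.5: RCTC Grade 4, not flagged.
- 9.5 − 7.8 = 1.7: RCTC Grade 3 on the absolute value, flagged.

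**Tests where the limits agree.** WBC (1.9 against < 2.0), neutrophils (0.9 against < 1.0), platelets (49.9 against < 50), low potassium (2.9 against < 3.0), glucose (39/18.016 = 2.16 against < 2.2; 251/18.016 = 13.93 against > 13.9 mmol/L) and low calcium (6.9/4.008 = 1.72 against < 1.75 mmol/L). The divisors are standard unit conversions.

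**Tests where the SAP is more sensitive.** High potassium (> 6.0 against 6.5) and low sodium (< 130 against 124), reading the appendix's unit label for both as mmol/L. High calcium, marginally (> 3.1 against 12.6/4.008 = 3.14 mmol/L). CK: the SAP flags any value above 5 times ULN, whereas RCTC Grade 3 needs more than 4 times with weakness. The SAP therefore gains asymptomatic rises and loses symptomatic ones between 4 and 5 times. It also adds limits for triglycerides, total cholesterol and high sodium, none of which has a row in the appendix as supplied.

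**Coverage.** SAP Tables 4 and 5 hold 12 + 5 = 17 tests. The appendix grades 5 haematology and 12 chemistry tests, also 17. Fifteen are common to both, including all seven in the table above. The SAP tables add triglycerides and cholesterol and omit LDH and uric acid, both of which are collected (SAP Table 3).

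**Do the other displays fill the gap?**
- Shift tables show that a reference limit was crossed, not by how much. A patient already low at baseline cannot count as a shift to low.
- Means, minima and maxima do not count patients.
- SAP 11.3 promises a listing of significant abnormal values, but the only threshold the SAP defines for one is CTCAE Grade 3+.
- Adverse event capture depends on the investigator judging the change clinically relevant (Protocol 5.2.2.1).
- The Hy's Law listing requires ALP below 2 times ULN. Take ALT 4, bilirubin 2.5 and ALP 2.5 times ULN. This meets the laboratory thresholds for the protocol's hepatic injury event (at least 3 and 2 times ULN) but misses Table 4, the Grade 3+ listing and the Hy's Law listing. RCTC grades both the ALT and the bilirubin as 3.

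**The case against.** The strongest reply is that the protocol's grading is largely kept. Protocol 5.2.3 requires RCTC only for values judged clinically relevant. Such values are recorded as adverse events, and SAP 11.2.1 tabulates those by maximum RCTC severity. Protocol 7.3.3 fixes no scale for the abnormality table, the SAP discloses its choice, and nothing is tested. WBC, neutrophil and platelet limits match RCTC. Liver injury has its own listing, expedited reporting and a set of hepatic search terms. All of this is correct, and it limits the point to the frequency tables and the Grade 3+ listing. It does not supply a count of patients by severity that is independent of investigator judgement.

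Three stronger readings are tempting, and the documents do not support them:
- A reader might infer that the severe values vanish from the report. They do not: they enter the summaries, extreme-value displays and shift tables, and the adverse event tables if clinically relevant.
- A reader might infer that the documents contradict the stated reason. That reason concerns the full CTCAE list, which the documents do not reproduce. Tables 4 and 5 are only a selection from it, so counting their rows cannot refute it.
- A reader might infer that the SAP is looser almost everywhere, or that its tables will show few or no notable values. Several limits are tighter or new, and no patient data are available.

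A practical objection also stands. The printed RCTC bands overlap at some edges (ALT 3.0 and ALP 3.0 each fall in Grades 2 and 3), and uric acid Grade 3 includes gout, a clinical criterion. Any added table needs a rule for these.

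**Conclusion.** The point holds in this limited form. For seven of 17 tests, Tables 4 and 5 and the Grade 3+ listing do not count values that the protocol's own scale grades as severe. For four of the seven the whole RCTC Grade 3 band is lost, and for haemoglobin some Grade 4 falls are lost too. Wider coverage is a reason to add CTCAE rows for tests RCTC lacks. It is not a reason for looser limits on tests RCTC already grades.

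The number of patients affected cannot be computed. Purely as an assumption, if 1%, 5% or 10% of the roughly 100 planned patients had a value in a missed band, about 1, 5 or 10 patients would go uncounted in these displays. The comparison rests on the appendix and tables as printed and on the unit readings stated above. This is a change that should be made. It does not undermine the planned analysis as a whole.

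**What to change.** Keep the CTCAE tables. In SAP 11.3.2:
- Add counts, percentages and a listing of subjects with post-baseline RCTC Grade 3 and Grade 4 values for lymphocytes, haemoglobin (including change from baseline), AST, ALT, total bilirubin, ALP and creatinine. The SAP's risankizumab baseline can serve for the haemoglobin change. LDH and the numeric uric acid limits are optional additions.
- State that a value on an overlapping band edge takes the higher grade. Because the bands are printed to one decimal, also state how values between bands are graded.
- State that for these seven tests the CTCAE cut-offs are less sensitive than RCTC Grade 3, so that readers can reconcile the laboratory tables with the adverse event tables.

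The data are already collected, so the cost is SAP wording, a few table rows and one listing. The downside is that more subjects will be shown with notable values.
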